6.5.2 Vital signs

Vital signs include BP and pulse measurements. After the patient has been sitting for five minutes, with back supported and both feet placed on the floor, systolic and diastolic blood pressure will be measured three times using an automated validated device, e.g. OMRON,

with an appropriately sized cuff. The repeat sitting measurements will be made at 1 - 2 minute intervals and the mean of the three measurements will be used. In case the cuff sizes available are not large enough for the patient's arm circumference, a sphygmomanometer with an appropriately sized cuff may be used.

Clinically notable vital signs are defined in [Appendix 1](#).

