The following analyses will be performed, where appropriate, for measurements of urinalysis, hematology and blood chemistry tests:

Standard descriptive statistics for values measured at baseline and post-baseline visits including changes from baseline, shift tables relative to the normal ranges between baseline and post-baseline visits, number (and percentage) of patients with clinically notable changes for selected tests.

[REDACTED]

[REDACTED]

[REDACTED]

Vital signs

Vital signs (i.e. blood pressure, pulse rate and) will be summarized with standard descriptive statistics of raw data and changes from baseline for each visit separately. The numbers of patients with vital signs meeting the definition of notably abnormal will be presented by parameter.

ECG

ECG data will be summarized by treatment and visit. Changes from baseline will be summarized.

Notable QTc values and change from baseline will be summarized. A notable value is defined as a QTc interval of greater than 450 ms. The categories used for the change (increase) in QTc are - less than 30 ms, 30 to 60 ms and greater than 60 ms.

The Fredricia QT correction formula (QTcF) will be used for clinical decisions.

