9.4.2 Statistical model, hypothesis, and method of analysis

No hypotheses will be tested.

Adverse events will be summarized by presenting the number and percentage of patients having any AE by primary system organ class and/or preferred term. AE by severity, drug related AEs, AEs leading to premature discontinuation of study drug, death and serious AEs will be presented in a similar format as all AEs.

AEs related to potential anaphylaxis will be summarized separately.

Laboratory and vital sign data will be summarized by presenting summary statistics of values and change from baseline by visit, and by presenting frequency of patients with clinically notable changes.

[figure not shown]
ECG intervals will be summarized by presenting summary statistics for change from baseline values by visit. Count and frequency of clinically notable ECG abnormalities or changes will be presented. The (uncorrected) QT interval will be corrected according to the Fridericia's formulae.

Laboratory data, vital sign data and ECG data will be listed with abnormal value flagged based on normal ranges or clinically notable ranges.

Other safety data will be summarized and listed as appropriate.

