13.1 Appendix 1: Clinically notable laboratory values and vital signs

Refer to [Appendix 2](#) for clinically notable serum blood chemistry tests for hepatotoxicity.

The following specific criteria have been identified for this study:

- AST, ALT or INR above 1.5x ULN
- Creatinine above ULN
- Platelets <75,000 μ L.
- Stool test result positive for ova or parasites

Any patient that has AST, ALT, INR or creatinine levels above the limits specified above or a stool test result positive for ova or parasites at Visit 206, should be excluded from the study.

[figure not shown]
Any patients that have AST, ALT, INR or creatinine levels above the limits specified above, after the patient has started treatment in the extension study, should have regular laboratory assessments to monitor those laboratory parameters, until they return to baseline values (or within normal range), or the investigator indicates that post baseline values are sufficiently close to baseline that no further follow-up is warranted for patient safety.

Any patients that have platelets <75,000 μ L after the patient has started treatment should be discontinued from study drug.

For all other laboratory assessments, the Central Laboratory will flag laboratory values falling outside of the normal ranges on the Central Laboratory Report (which the investigator should review and sign-off) and the investigator will report any values considered clinically significant in the eCRF.

Notable values for vital signs and change from baseline will be summarized. A notable value is defined as follows: heart rate of <40 and >90 bpm; systolic blood pressure of <90 and >140 mmHg; diastolic blood pressure of <65 and >90 mmHg.

For ECGs a notable QTc value is defined as a QTc (Fridericia's) interval of greater than 450 ms for males and > 460 for females – all such ECGs require assessment for clinical relevance by the Investigator. Patients with a heart rate of >100 bpm measured on 2 occasions, approximately 10 minutes apart, while resting, should be discontinued from study treatment.

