2.5 Analysis of the primary objective

The primary objective of this study is to obtain data on the long-term safety and tolerability of QGE031 for 12 months of treatment in CSU patients.

The primary variables which will be analyzed are: for AEs/ Serious Adverse Events (SAEs), ECGs, laboratory assessments, vital signs data and events of special interest such as hypersensitivity reactions, anaphylaxis, cardio-cerebrovascular events, and pre-malignancies and malignancies.

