2.5.3 Vital signs

Vital signs (i.e. blood pressure and pulse rate) will be summarized by presenting summary statistics of values and change from baseline by visit. Change from baseline will only be summarized for patients having both baseline and post-baseline values. In addition, frequency of patients with clinically notable values will be presented for both the treatment and follow-up epochs. Patients with notable vital signs as defined below will also be listed.

A notable value is defined as follows:

- Pulse rate below 60 bpm (bradycardia)
- Pulse rate above 100 bpm (tachycardia)
- Systolic blood pressure (SBP) greater than or equal to 140 mmHg
- SBP lower than 90 mmHg
- Diastolic blood pressure (DBP) greater than or equal to 90 mmHg
- DBP lower than 60 mmHg.

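### SAP 2.5.3 counts patients with notable vital signs under limits that differ, at five of six cut-offs, from the protocol's Appendix 1 definition

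*SAP*

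**What the plan says.** **Protocol.** Section 6.5.2 sets the scope, "Vital signs include BP and pulse measurements", and points to Appendix 1 for the definition: "Clinically notable vital signs are defined in" that appendix. Appendix 1 (13.1) states "Notable values for vital signs and change from baseline will be summarized" and then gives the limits: "heart rate of <40 and >90 bpm; systolic blood pressure of <90 and >140 mmHg; diastolic blood pressure of <65 and >90 mmHg". Section 9.4.1, among the primary variables, commits to a patient count: "The numbers of patients with vital signs meeting the definition of notably abnormal will be presented by parameter". Section 9.4.2 adds a listing rule: "Laboratory data, vital sign data and ECG data will be listed with abnormal value flagged based on normal ranges or clinically notable ranges".

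**SAP.** Section 2.5 repeats the primary variables, including "laboratory assessments, vital signs data and events of special interest". Section 2.5.3 plans the frequency of patients with notable values in the treatment and follow-up epochs, plus a listing of those patients, and supplies its own definition. It starts with "Pulse rate below 60 bpm (bradycardia" and continues with pulse above 100, SBP at or above 140 or below 90, and DBP at or above 90 or below 60.

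**Declared changes.** No readable entry in SAP section 4 mentions vital-sign limits. Some entries there are redacted.

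**The concern.** The protocol has one definition of a notable vital sign, and Appendix 1 itself ties it to a summary. The SAP produces that summary with different limits. It does not set Appendix 1 aside elsewhere: its laboratory criteria in 2.5.2 include the Appendix 1 platelet, AST/ALT/INR, creatinine and stool criteria, and its QTcF limits in 2.5.4 match Appendix 1 by sex. Among these definitions, vital signs alone depart.

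At stake is a descriptive result for a primary variable. There is no comparator arm and no hypothesis test, so a percentage of patients with notable values is taken at face value and depends directly on the cut-offs. The differences run in both directions, so neither set is simply stricter and a reader cannot convert one count into the other.

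**Working it through.** The plan states no figure to reproduce. The check sets the two definitions side by side, derives the direction of each difference, and then illustrates its size.

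**Step 1. The limits** (protocol Appendix 1 and SAP 2.5.3)

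| Limit | Protocol | SAP | Notable under one only | SAP count, same data |
|---|---|---|---|---|
| Low pulse (bpm) | <40 | <60 | SAP: 40 to below 60 | equal or higher |
| High pulse (bpm) | >90 | >100 | protocol: above 90 up to 100 | equal or lower |
| Low SBP (mmHg) | <90 | <90 | none | the same |
| High SBP (mmHg) | >140 | >=140 | SAP: exactly 140 | equal or higher |
| Low DBP (mmHg) | <65 | <60 | protocol: 60 to below 65 | equal or lower |
| High DBP (mmHg) | >90 | >=90 | SAP: exactly 90 | equal or higher |

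The directions need no assumption: each pair of limits is nested, so every patient counted under the narrower one is counted under the wider one.

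**Step 2. One reading** (assumed normal, whole-number values; Φ is the standard normal distribution function)

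Pulse, mean 72, SD 10:
- Low, protocol: Φ((39.5 − 72)/10) = Φ(−3.25) = 0.0006. Low, SAP: Φ((59.5 − 72)/10) = Φ(−1.25) = 0.1056.
- High, protocol: 1 − Φ((90.5 − 72)/10) = 1 − Φ(1.85) = 0.0322. High, SAP: 1 − Φ((100.5 − 72)/10) = 1 − Φ(2.85) = 0.0022.

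DBP, mean 78, SD 9:
- Low, protocol: Φ((64.5 − 78)/9) = Φ(−1.50) = 0.0668. Low, SAP: Φ((59.5 − 78)/9) = Φ(−2.06) = 0.0199.

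**Step 3. Any notable value per patient**

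Patients are measured repeatedly, so the count depends on the number of visits. Protocol Table 6-1 gives 13 post-baseline visits to Week 52 (302–313 and 401) and five in follow-up (401–405). The model is value = m + s(√ρ·u + √(1 − ρ)·e), with u drawn once per patient and e once per visit, both standard normal, rounded to thirds as for a mean of three readings. Assumptions:
- pulse: m 68, 72, 76; s 8, 10, 12
- DBP: m 74, 76, 78; s 7, 9, 11
- SBP: m 120, 124, 128; s 12, 14.4, 17
- ρ 0.4, 0.5, 0.6; no dropout

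This gives 3 × 3 × 3 = 27 scenarios per parameter, with 100,000 simulated patients each. Ranges across scenarios:

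| Limit | 13 visits, protocol | 13 visits, SAP | 5 visits, protocol | 5 visits, SAP |
|---|---|---|---|---|
| Low pulse | 0–9% | 13–79% | 0–4% | 7–60% |
| High pulse | 2–55% | 0–17% | 1–36% | 0–9% |
| Low DBP | 17–72% | 4–50% | 10–53% | 2–31% |

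SAP minus protocol within the same scenario, over 13 visits and per 240 patients (the expected enrolment): low pulse +31 to +169, high pulse −92 to −5, low DBP −77 to −31.

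**Step 4. The boundary alone**

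Over 13 visits, >= in place of > adds 0.8–1.4 percentage points for high SBP and 0.8–2.0 for high DBP with values in thirds. With whole-number values it adds 2.3–4.4 and 2.4–6.3.

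**Step 5. Sensitivity, low pulse, protocol vs SAP**
- Visit 401 counted only as follow-up, leaving 12 treatment visits: 0–8% vs 12–77%.
- Whole-number pulse, 13 visits: 0–8% vs 12–77%.
- Only patients not notable at baseline counted: about 0–8% vs 11–55%.

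**The case against.** **The link to Appendix 1 is indirect.** Section 6.5.2 mentions no count, the vital-signs paragraph of 9.4.1 names no appendix, and 9.4.2 speaks of notable changes. This is accurate, but the link holds: 9.4.1 relies on a definition, the protocol contains only one, 6.5.2 points to it, and Appendix 1 says the values will be summarized.

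**The change may already be declared.** Entries in SAP section 4 are redacted, so non-disclosure cannot be shown. This stands, and that part of the fix is conditional.

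**The consequences are limited.** By-visit values and changes from baseline do not use these limits, no hypothesis is tested, the interim analysis alters no procedures, and the SAP prints its own limits. Section 9.4.2 lets the listing flag on normal or notable ranges, so the listing is not itself a departure. All of this stands and bounds the severity, but the count remains different from the one promised.

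**A cut at 100 bpm is not foreign to the protocol.** Appendix 1 uses a heart rate above 100 in a rule for discontinuing treatment. That rule is separate and does not define the notable count.

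**The size is weakly known.** Every mean, SD and correlation is assumed and the ranges are wide. Counting only new occurrences, as the SAP does for laboratory and ECG abnormalities, lowers the upper end for low pulse. The > versus >= differences are small with the mean of three readings that 6.5.2 prescribes for blood pressure. These points stand: the size is illustrative and only the direction is certain.

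**Conclusion.** The concern holds. The material differences are both pulse limits and the low DBP limit; the high SBP and high DBP differences affect only values exactly at the boundary. The conclusion and the direction of each shift follow from the limits alone. The size rests entirely on the assumed distributions, and in all 27 scenarios the shift in low pulse, high pulse and low DBP is visible at the planned enrolment. The effect is confined to the notable-value count and the listing that shares its limits. It should be corrected, but it does not undermine the rest of the safety analysis.

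**What to change.** Reconcile SAP 2.5.3 with protocol Appendix 1 for the notable-value count, including > versus >=, and use the reconciled limits in the listing that shares them.

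If the different limits are intended and no redacted entry already covers them, declare and justify the change in SAP section 4. Showing the count under the Appendix 1 limits alongside is then advisable, so that the promised result is also available; the finding does not depend on it. Which limits are clinically right is for the sponsor to settle.

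The cost is SAP wording and a parameter change in one table and its listing, or one extra set of columns in that table if both counts are shown.

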2.5.4 ECG

ECG intervals will be summarized by presenting summary statistics for values and change from baseline values by visit. ECGs are planned to be performed in triplicate (other than baseline ECG results, which has been collected once), therefore the mean of the patients' scheduled measurements, by visit, will be used in the summary statistics.

Count and frequency of clinically notable ECG abnormalities or changes will be presented for patients with newly occurring or worsening notable abnormalities occurring post-baseline. For

ECGs, a notable corrected QT Interval (QTc) value is defined as a QTcF (Fridericia's) interval of greater than 450 msec for males and greater than 460 msec for females. The categories used for the change (increase) in QTcF are - greater than 30 msec and greater than 60 msec.

ECG evaluation for all subjects with at least one visit, with the most common interpretation of that visit is abnormal, will be listed. ECG interval data will be listed for all patients and abnormal value flagged based on clinically notable ranges.

A shift table from baseline to the worst post-baseline value will be presented based on the overall ECG interpretation.

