3.1 Study design

[figure not shown]
This study is an open label, single arm, long-term safety extension for all patients who completed the core study CQGE031C2201 and fulfil the enrollment criteria for the extension study.

Among the 360 patients expected to participate in the core study, it is estimated that approximately 240 subjects may enroll in this extension study. Enrollment criteria require subjects to complete the treatment epoch and at least visit 201 - 203 in the follow-up epoch in study CQGE031C2201 and present with active disease, as defined by $UAS7 \geq 12$. The study consists of two epochs: open-label treatment and post-treatment follow up epoch. At or after visit 203, when the subjects become eligible to enroll in this extension study, they will complete all assessments associated with Visit 206 as a part of core study completion. The treatment epoch of this extension study will consist of 52 weeks of QGE031 240 mg s.c. at 4-week intervals. During the post-treatment follow-up epoch, the patients will be followed at 12-week intervals for 48 weeks. See [Figure 3-1](#) for study design.

As in the core study, patients will continue using their background medication i.e H1-AH at approved or increased doses alone or in combination with H2-AH and/or a LTRA.

Open-label study Treatment Epoch:

- Visit 301 - 313
- This treatment epoch consists of 52 weeks of open label treatment with QGE031 240mg sc every 4 weeks.
- All lab assessments done as a part of end of core study visit (Visit 206) will be used to determine eligibility to enroll into the extension study.

[figure not shown]

- The informed consent will be signed at visit 206
- The subjects will continue to complete eDiary assessments between visits 206 and 301
- Visit 301 should occur approximately 14 - 21 days after visit 206 core study assessments. Only in exceptional circumstances, when information concerning eligibility is outstanding (e.g., pending laboratory data), visit 301 can be extended.
- Subjects relevant medical conditions and concomitant medications will be reviewed at visits 206
- Subjects receive their first dose of QGE031 at visit 301 and last dose of QGE031 at visit 313

Post-treatment follow-up Epoch:

[figure not shown]
- Visit 401 – 405
- 48 weeks of post-treatment follow up consisting of visits every 12 weeks.

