6.5.5 Electrocardiogram (ECG)

Standard 12 lead ECGs must be performed only after subjects have been resting in the supine position for at least 10 minutes. The preferred sequence of cardiovascular data collection during study visits is to perform the ECG prior to vital signs, and blood sampling. The Fridericia's QT correction formula (QTcF) should be used for clinical decisions.

Triplicate ECGs (3 ECG measurements taken at approximately 1 min intervals) will be recorded at Visits 206, 313 and 405. For patients whose ECG is abnormal at Visit 206 due to technical/mechanical faults, a repeat ECG may be performed. All electrocardiograms must be performed using a 12 standard lead. For those patients who prematurely discontinue from the study, an ECG tracing will be taken at Visit 405.

For each ECG performed original traces and identical duplicate traces will be produced. The original trace will be sent electronically to the CRO directly from the provided ECG machine. Two 'identical' duplicate print-outs will be generated and kept at the investigator site as source documentation and as back-up for submission to the vendor in case of problems with the electronic transmission. The 'identical' duplicates kept at the investigator site will be dated and signed and will be archived at the study site. The subject's number, subject initials, the date, actual time of the tracing, and Study Code (CQGE031C2201E1) must appear on each page of the ECG tracing.

Full details of all procedures relating to the ECG collection and reporting will be contained in an investigator manual to be provided by the CRO to each investigator site.

Clinically significant ECG findings prior to dosing with investigational treatment must be discussed with the sponsor.

Clinically significant abnormalities should be recorded on the relevant section of the medical history/Current medical conditions if present at visit 206 or on the AE eCRF page as appropriate.

[REDACTED]

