2.1.1 Assessment windows

No assessment windows are defined for this study. Consequently, all by-visit summaries will be performed as per below scheduled visits.

Table 1-1 Assessment windows for scheduled visits

Analysis Visit	E1 Week	E1 Scheduled Day	Visit Window
E1 Baseline	Baseline	-21/-14, 1	Up to Day 1
E1 Week 4	4	29	NA
E1 Week 8	8	57	NA
E1 Week 12	12	85	NA
E1 Week 16	16	113	NA
E1 Week 20	20	141	NA

E1 Week 24	24	169	NA
E1 Week 28	28	197	NA
E1 Week 32	32	225	NA
E1 Week 36	36	253	NA
E1 Week 40	40	281	NA
E1 Week 44	44	309	NA
E1 Week 48	48	337	NA
E1 Week 52	52	365	NA
E1 Week 64	64	449	NA
E1 Week 76	76	533	NA
E1 Week 88	88	617	NA
E1 Week 100	100	701	NA

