2.4 Treatments (study treatment, rescue medication, concomitant therapies, compliance)

2.4.1 Study treatment / compliance

Patients will receive two subcutaneous injections every 4 weeks at 13 visits during the open label treatment epoch (i.e. at Day 1, Week 4, Week 8, Week 12 to Week 48).

Compliance is assured as study drug needs to be administered by study personnel every 4 weeks via subcutaneous injection. Administration of study drug, date, time and injection site will be recorded in the source documents and on the Drug Administration Record eCRF for each injection.

The analysis of study treatment data will be based on the Safety set.

The duration of exposure to study treatment in weeks will be summarized by Safety set. Duration of exposure is defined as the date of the last treatment minus the date of first extension study drug administration plus 4 weeks (28 days).

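### The notable-ECG counts and the ECG shift table pool the last-dose visit with a visit 52 weeks later, although the matching laboratory and vital-sign outputs are split by epoch

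*SAP*

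**What the plan says.** SAP 2.5.4 plans two categorical ECG outputs. The first is the outlier count: "Count and frequency of clinically notable ECG abnormalities or changes will be presented for patients with newly occurring or worsening notable abnormalities occurring post-baseline". It covers QTcF above 450 msec (males) or 460 msec (females), and increases above 30 and 60 msec. The second is the shift table: "A shift table from baseline to the worst post-baseline value will be presented based on the overall ECG interpretation". Neither is divided by epoch.

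The same section also summarises ECG values and changes from baseline by visit, using the mean of the replicates. It lists interval data for every patient, with notable values flagged.

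The matching outputs elsewhere in the SAP are divided. For vital signs (SAP 2.5.3), "frequency of patients with clinically notable values will be presented for both the treatment and follow-up epochs". For laboratory data (SAP 2.5.2), the shift tables, the notable counts and the liver criteria are each given once for treatment and once for follow-up.

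On collection, Protocol 6.5.5 says: "Triplicate ECGs (3 ECG measurements taken at approximately 1 min intervals) will be recorded at Visits 206, 313 and 405". SAP 2.5.4 instead describes the baseline ECG as a single recording, with triplicates only afterwards.

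**The concern.** ECG change is named in the primary objective (Protocol 2.1, SAP 1.2.1). A reader of the report will take the count of notable QTcF values as a statement about patients on QGE031. As planned, one of the two scheduled visits feeding that count comes about a year after dosing has stopped, and the table does not show which visit produced a case.

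An abnormality first seen at Visit 405 would, if reported as an adverse event on the planned schedule, fall outside the treatment-emergent window of SAP 2.5.1. It would still sit in the ECG count next to on-treatment cases. SAP 2.6.10 records 17 patients who took omalizumab after treatment, and SAP 2.5.6 keeps their safety data, so some follow-up ECGs may also come after another anti-IgE drug was started.

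A second issue is that the reading rule is open. The visit mean is prescribed for the summary statistics only. For the outlier counts the SAP does not say whether the mean or any one tracing applies. For the shift table it does not say whether the worst value is taken over visit-level interpretations or over individual tracings. Two programmers could produce different tables from the same data.

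**Working it through.** The documents give no ECG event rate, so there is no planned figure to reproduce. The timing can be checked exactly; the size can only be illustrated.

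**Timing**

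- Last dose: Protocol 3.1 says "Subjects receive their first dose of QGE031 at visit 301 and last dose of QGE031 at visit 313". SAP 2.4.1 gives 13 dosing visits, "i.e. at Day 1, Week 4, Week 8, Week 12 to Week 48". The 13th dose is on Day 1 + 12 × 28 = 337.
- Final ECG visit: the SAP 2.1.1 schedule row reads "E1 Week 100 100 701 NA", that is, Day 701.
- Gap: 701 − 337 = 364 days = 52 weeks.
- The treatment-emergent window in SAP 2.5.1 closes 16 weeks after the last dose. 52 − 16 = 36 weeks beyond it. SAP section 4 restates the 16-week limit but also carries a bullet without it; the 2.5.1 text is used here.

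Of the two scheduled post-baseline ECG visits, one is in the treatment epoch and one is far outside it.

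**Effect of pooling on the count**

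Let p be the proportion of patients notable at each visit (assumed), with N = 240 (the enrolment expectation in Protocol 9.7). The Visit 313 count is N × p. The pooled count runs from N × p, if the same patients are notable at both visits, to N × [1 − (1 − p)²], if the visits are independent. For p = 2%: 1 − 0.98² = 3.96%, and 240 × 0.0396 = 9.5.

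| Assumed p per visit | Visit 313 alone | Pooled, full overlap | Pooled, independent |
|---|---|---|---|
| 1% | 2.4 | 2.4 | 4.8 |
| 2% | 4.8 | 4.8 | 9.5 |
| 5% | 12.0 | 12.0 | 23.4 |
| 10% | 24.0 | 24.0 | 45.6 |

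With equal rates at the two visits, pooling at most about doubles the count. Because exclusion criterion 16 keeps out patients with a confirmed QTcF above these limits at Visit 206, nearly every later notable value will count as new.

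**Effect of the reading rule**

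A simulation of 400,000 patients with no drug effect gives the share with a QTcF increase above 30 msec over a single baseline tracing. All inputs are assumed: mean 410 msec, between-patient SD 15, visit SD 6 to 12, replicate SD 4 to 8, baseline at or below 450 msec.

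| Rule | Share of patients |
|---|---|
| Visit 313 mean | 0.1% to 6.2% |
| Either visit mean | 0.2% to 10.5% |
| Any of six tracings | 0.7% to 19.9% |
| Visit 313 mean, triplicate baseline | 0.04% to 5.1% |

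The absolute rates depend on the assumed SDs. The ordering shows why the rule and the number of baseline tracings need to be stated.

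**The case against.** The strongest reply is that the plan already lets the last-dose visit be read alone. Interval values and changes are summarised by visit, listings flag notable values, and the interim summary (SAP 2.8) includes ECG data once all patients have finished treatment. This stands, and it limits the defect to two outputs. It does not remove it: a by-visit mean can conceal a few large QTcF increases, which is what the outlier count is for, and early enrollees may already have follow-up ECGs at the interim.

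A reader might go further and infer that the primary ECG result cannot be related to exposure at all. The by-visit summaries contradict that. In a single-arm study with no hypotheses, a split would not establish causation either.

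A reader might also infer that pooling could hide an on-treatment signal. It cannot. The count is a union over visits and the shift table keeps the worst value, so every Visit 313 abnormality is retained and pooling only adds.

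A reader might infer that the SAP prescribes the worst of six tracings. It does not. For the counts no rule is given. For the shift table, the overall interpretation can as naturally mean the worse of two visit-level reads, since the section already uses a majority read per visit to select patients for a listing. Large inflation figures built on a worst-of-six rule therefore have no support in the text.

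Finally, follow-up is meant to assess safety after treatment stops (Protocol 3.2), so an all-post-baseline table has a legitimate use. That is a reason to keep it as an addition, not as the only presentation.

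**Conclusion.** The point holds for the notable-ECG counts and the ECG shift table only. They combine the last-dose visit with one that is 364 days later on the planned schedule, against the SAP's own convention for laboratory and vital-sign data. The consequence is a count that may overstate on-treatment abnormalities: for an assumed 2% per visit, between 4.8 and 9.5 of 240 patients where Visit 313 alone would give 4.8. The upper end needs independent visits, and correlation within patients lowers it.

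Two limits apply. The 52-week gap does not hold for everyone: patients who stop treatment early have Visit 313 four weeks after their last dose (Protocol 5.6.2), and premature withdrawals have their ECG under Visit 405 (Protocol 6.5.5), which may come sooner. And the split shows when an abnormality arose, not whether the drug caused it.

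Separately, the protocol and the SAP disagree on the number of baseline ECGs, and that affects every change from baseline.

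**What to change.** In SAP 2.5.4:

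- Present the notable QTcF counts, the increases above 30 and 60 msec, and the interpretation shift table separately for the treatment epoch and the follow-up epoch, as SAP 2.5.2 and 2.5.3 do. Keep the pooled version as an additional row if wanted.
- State whether the visit mean or a single tracing defines a notable QTcF or a notable increase, and whether the shift table uses the visit-level interpretation. A visit-level rule matches the summary statistics but leaves an isolated abnormal replicate to the listing; a single-tracing rule catches it but counts more chance findings. Either is workable if stated.
- Reconcile the single baseline ECG in the SAP with the triplicate required at Visit 206 in Protocol 6.5.5, and say which baseline value is used.
- Note in the table footnote that time since last dose varies for early discontinuers and premature withdrawals.

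The cost is a few sentences and an extra set of columns in two tables. No data collection changes.
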